### **6.4.2. Activities performed by sponsor representatives**

Sponsor (Clinical Manager or a representative hereof) is responsible for:

- Training of investigator and study personnel in the informed consent procedure, study procedures, how to use the products, complete the CRF, how to report possible safety issues and in ISO 14 155. All training will be documented.
- Support during the recruitment process and conduct of the investigation
- Monitoring

### **6.4.3. Foreseeable factors that may compromise the outcome / results**

No foreseeable factors are expected to compromise the outcome/results of the design.

#### 6.4.4. Flow-chart

	PERFORMED BY	SOURCE	INFORMATION AND INCLUSION VISIT 0	VISIT 1	TERMINATION END OF VISIT 1
General					
Oral information	Investigator	NA	X		
Signed informed consent	Subject	Informed consent form	X		
Signed Letter of authority	Subject	Letter of Authority Form	X		
Signed secrecy agreement	Subject	Secrecy form	X		
Concomitant medication registered	Investigator	CRF	X		
Check of in- and exclusion criteria	Investigator	CRF	X		
Allocation to subject number and sensor serial number	Investigator	CRF	X		
Insurance of subjects well-being and compliance with CIP	Investigator	CRF	X	X	X
Registration of Baseline data					
Date of birth	Investigator	CRF		X	
Gender	Investigator	CRF		X	
Check for symptoms of UTI before catheterisation					
Check for symptoms of UTI (frequent urination, stinging and pain at urination)	Investigator	CRF		X	
Catheterisation	Investigator	CRF		X	
Registration of measurements					
Sensor data prior to and during voiding.	Investigator	Data points		X	
Urine flow profile (uroflowmeter) - Max flow rate (mL/s) - Middle flow rate (mL/s) - Voiding time (s) - Flow time (s) - Time to max flow (s) - Voided volume (mL)	Investigator	Printed graph		X	
AEs/ADEs/SAEs/SADEs	Investigator	CRF		X	X
Registration of termination					
Termination form. Completed	Investigator	CRF			X

Table 1 chart showing the connection between visits and assessments

### 6.4.5. Case Report Forms

The CRFs are printed and supplied by sponsor and one CRF is provided for each subject. It is the responsibility of the Investigator that all data are entered promptly and correctly.

Each CRF has an identification number and a printed instruction for completion.

The sponsor will be responsible for training the investigator and the study nurse in completion of the CRF.

The CRF will clearly state which parts are to be completed by whom.

It will be the responsibility of investigator that all measurements and observations are correctly noted with a pen (permanent writing utensil) in the CRF.

Any correction in the CRF must be clearly signed and dated by authorised site personnel. The entry corrected must be crossed out so that the entry is still legible.

#### Example 1:

2010-11 [name]  
2011

07	JAN	2011
Day	Month	Year

Ex AUG

#### Example 2:

	No	Yes
2010-11 [name]		

Figure 2 Two examples of how to make corrections in the CRF

The investigator will keep a separate list with the subject ID numbers, names and addresses in a locked room. Only data referred to in this clinical investigation plan will be recorded in the CRFs.

### 6.4.6. Supplementary materials and equipment

Supplementing devices or instruments normally used for catheterisation (e.g. medical gloves, tray for urine collection), uroflow meter and CE-marked commercial available catheters SpeediCath® Standard, male/female, Nelaton tip.

## 6.5. Monitoring Plan

During the period of the investigation monitoring is planned and carried out by the Clinical Manager.

Before doing any review of subject data, the Clinical Manager must review the signed Informed Consent Form(s) and only monitor data from subjects with a correct signed Informed Consent Form.

The first monitoring visit at the site should be conducted as soon as reasonably possible after the first subject at the site has completed the first visit of the investigation to minimise systematic errors done by site.

Additional monitoring will be conducted in accordance to the recruitment rate:

- Monitoring visit two will be completed as soon as possible after the last subject has completed the investigation
- Monitoring visit three, Close out visit, will be conducted as soon as possible after LSO

Signed informed consent, signed Letter of authority, in- and exclusion criteria and all Adverse events occurring in the investigation will be 100% monitored for all subjects enrolled in the investigation.

Investigation Site File shall be monitored for 100% completion per the Investigation File Requirement Checklist.

Monitoring activities conducted by the clinical manager will be documented in the site visit report applicable to the conducted visit. A summary describing the observation(s) and actions required shall be provided as soon as reasonably possible to the investigator after the conducted monitoring visit. The sponsor representative will have close contact to the site in the recruitment period to ensure that any concerns, problems or recruitment challenges are solved with the site in a timely manner.

### 6.5.1. Source data verification

Source data verification will be performed to the extent it is possible.

The Source Data Specification Form must be completed at the initiation visit detailing the location of the source data for each data point.

For each catheterisation, pressure and flow measurements will be graphically presented over time and the data quality visually evaluated and will be filed on a secure data drive

Data points for data verification:

- Informed Consent Forms
- Letter of Authority
- In- / Exclusion criteria
- Concomitant medication
- AE/ADE
- other

The informed consent forms must be 100% verified for timely completeness.

The Letter of Authority form must also be 100% verified for timely completeness.

Only the investigator, delegated site personnel and the sponsor representatives will have access to all the CRFs. The subject will have access to his/her own CRF.

### 6.5.2. Other methods for data quality assurance

The sponsor, sponsor's representative and/or investigational sites may be inspected by competent authorities or their representatives and likewise may be audited per Coloplast A/S internal quality audit plan and procedures.

## 7. Statistical considerations

### 7.1. Statistical design, method and analytical procedures

Data will be presented using SAS version 9.4 (SAS Institute Inc., Cary, NC).

Exploratory qualitative analysis will be performed with other software that allows for graphic presentations.

Baseline data will be summarised and listed.

#### Definition of analysis populations

The intention to treat population (ITT) is included in the full analysis set (FAS).

The ITT population will be constituted by subjects who:

- Have provided valid informed consent
- Have valid information for at least one of the endpoints

Invalid individual data points may be omitted from analysis even though the corresponding subject is part of the ITT population. Any exclusion of data points will be documented.

The safety population is basis for presentation of AEs and will be included in the safety analysis set (SAS).

The safety population constitute subjects who

- have given informed consent.

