### Background

Intermittent catheterisation is the preferred method of bladder emptying for persons with chronic urine retention due to neurogenic bladder dysfunction following e.g. spinal cord injury, or due to an enlarged prostate, etc. Coloplast A/S manufactures different catheters and devices for incontinence and works continuously to improve them.

The purpose of this study is to test the pressure sensor capabilities in a clinical environment. The sensor has shown good readable results in pre-clinical tests. Given the complex pressure conditions in the human body with pressure contributions from e.g. body movement, bowel peristalsis, heartbeat etc, the next step is to test the sensor capability to generate readable pressure measurement before and during catheterisation in healthy volunteers and to evaluate the extent of artifacts on the sensor readings.

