## 5. Objectives and hypotheses of the clinical investigation

### 5.1. Objective

The objective is to explore data obtained from a sensor connected to an intermittent catheter prior to and during voiding.

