## 6. Design of the clinical investigation

### 6.1. General

This clinical investigation is based on an open explorative design evaluating the sensor ability to record readable data in healthy volunteers and the extend of artifacts influencing data quality and readability in healthy volunteers.

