### **6.1.1. Primary endpoint**

#### **Primary endpoint**

Sensor capability to generate a readable sensor profile.

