#### **Analysis of primary endpoint**

Sensor data will be graphically presented over time and sensor capability to generate a readable sensor profile will be visually evaluated (FAS) and considered versus what is known on bladder physiology.

In case of an unexpected profile, the sensor profile will be considered in relation to the data on urine flow and voided volume, obtained via a standard uroflow meter.

Readable sensor profiles versus non-readable sensor profiles will be summarized.

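### Does the rule for omitting invalid data points let artifact be edited out before a sensor trace is judged readable?

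*Combined protocol and SAP*

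**What the plan says.** **The omission rule.** Section 7.1, under the definition of analysis populations, admits a subject to the ITT population on valid consent plus valid information for at least one endpoint. It continues: "Invalid individual data points may be omitted from analysis even though the corresponding subject is part of the ITT population". The next sentence is the safeguard: "Any exclusion of data points will be documented". No criterion for invalidity is given, and sensor data are not mentioned.

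**The interest in artifact.** The synopsis background, repeated in Section 3, gives as part of the purpose "to evaluate the extent of artifacts on the sensor readings". Section 6.1 describes the design as also evaluating "the extend of artifacts influencing data quality and readability in healthy volunteers". The formal objective in Section 5.1 does not name artifact: "The objective is to explore data obtained from a sensor connected to an intermittent catheter prior to and during voiding". Nor does the primary endpoint: "Sensor capability to generate a readable sensor profile".

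**The analysis.** In Section 7.1 the sensor data are graphed over time and judged by eye in the FAS, and then "Readable sensor profiles versus non-readable sensor profiles will be summarized". Section 6.5.1 adds: "For each catheterisation, pressure and flow measurements will be graphically presented over time and the data quality visually evaluated", with the results filed on a secure drive.

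**The concern.** Sensor values distorted by movement, peristalsis or the heartbeat are the ones an analyst might be most tempted to call invalid. They are also what the study wants to learn about. Section 7.1 does not say that readability is judged on the trace as recorded, and it names no summary of artifact. On a literal reading, someone could delete the disturbed values, look at the smoother curve, call it readable and stay within the plan. The readable count would then describe an edited trace and not the sensor's own output, and the artifact would survive only in the list of exclusions. Since the synopsis expects the data to guide development of the sensor, a flattering count could mislead the people who use it.

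**Working it through.** The plan has no figure to reproduce. The 12 subjects in Section 7.2 are an assumption, and there is no target rate, error rate or planned confidence interval. The check is mainly one of reading, followed by a bound on the size.

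**Step 1: does the rule reach single sensor values?** It sits directly after the criterion that valid information on one endpoint is enough for entry. There are two endpoints, readability and adverse events. The natural sense is that a subject who enters on one endpoint may still have an invalid observation on the other left out. Section 6.5.1 also uses the term data points for whole items, such as consent forms, concomitant medication and adverse events. Against this, the flow-chart in Section 6.4.4 gives data points as the source of the sensor data. That is a source label, alongside a printed graph for the uroflowmeter, and does not define the term for Section 7.1. The value-by-value reading is possible but is not stated.

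**Step 2: is artifact invalid?** Nothing in the plan says so. The background treats these disturbances as contributions to the pressure, present in the body and to be evaluated. The reading that fits the synopsis, Section 3 and Section 6.1 is that artifact is valid data of interest.

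**Step 3: is any editing described?** No filtering, smoothing or cleaning of traces appears anywhere. An unexpected profile is to be considered against urine flow and voided volume, so it is interpreted and not trimmed. Section 7.1 also plans exploratory qualitative graphics. Together with the data-quality assessment in Section 6.5.1, these give the artifact question a place, though not by name.

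**Step 4: how large could the effect be?** Let k be the assumed number of traces readable only after editing, with all others readable and n = 12.

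- Unedited proportion: (12 − k)/12. Edited proportion: 12/12. Shift: k/12.
- Exact (Clopper-Pearson) 95% limits for x of n, when x < n: the 0.025 quantile of Beta(x, n − x + 1) and the 0.975 quantile of Beta(x + 1, n − x). For x = n the lower limit is 0.025^(1/n); for 12/12 it is 0.025^(1/12) = 0.735.

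| k | Unedited | Exact 95% interval | Edited | Shift (points) |
|---|---|---|---|---|
| 0 | 12/12 = 100% | 73.5–100% | 12/12 | 0 |
| 1 | 11/12 = 91.7% | 61.5–99.8% | 12/12 | 8.3 |
| 2 | 10/12 = 83.3% | 51.6–97.9% | 12/12 | 16.7 |
| 3 | 9/12 = 75.0% | 42.8–94.5% | 12/12 | 25.0 |

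If a whole recording were omitted instead, 11/12 would become 11/11 (71.5–100%), the same 8.3 points for one subject. But the planned summary has a non-readable class, and a failed recording belongs there. Treating it as invalid would empty the class that the summary exists to count.

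**The case for a change.** The strongest case is that documenting an exclusion makes it traceable but sets no criterion, names no one to decide and does not fix which trace is rated. The flow-chart uses the rule's own term for the sensor data. Section 6.1 ties artifact directly to readability, which is the primary endpoint, so the absence of artifact from the formal objective is weak comfort. Filing the plots does not guarantee that they are unedited. The remedy would be a few sentences and no extra data from subjects.

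Much of this is true as a description of the text: invalid is undefined, and no sentence says that readability is judged on the unedited trace. What does not follow is that the plan directs or expects editing. Omission is optional, and every omission leaves a record from which the count can be rebuilt. An analyst who reads the purpose and the primary analysis together would plot what the sensor recorded and note the artifact. The change also has a price: Section 9 gives changes to assessment methods as an example of a significant change, so an amendment with notification or approval might be needed. A blanket exemption of sensor values would also keep genuine acquisition errors in the analysis.

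**Conclusion.** The ambiguity is real, but it is not a contradiction between rule and aim, and no bias has been shown. Followed as written, the plan gives a sound readable/non-readable count on about 12 plotted and filed traces, with any exclusion on record. The possible distortion is 8.3 percentage points per trace that depends on editing, and zero if none does; the counts of 1 to 3 are assumed because the documents give no rate. The intervals are illustrative and belong to no planned analysis. Section 7.4 applies no pass/fail criterion, so no decision rule or error rate is affected. The conclusion rests on analysts taking the plan's purpose at its word: artifact is noted and not deleted, and a failed recording is counted as non-readable. This is missing detail that competent analysts would fill sensibly, and the plan need not change.

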#### **Analysis of primary endpoint**

Sensor data will be graphically presented over time and sensor capability to generate a readable sensor profile will be visually evaluated (FAS) and considered versus what is known on bladder physiology.

In case of an unexpected profile, the sensor profile will be considered in relation to the data on urine flow and voided volume, obtained via a standard uroflow meter.

Readable sensor profiles versus non-readable sensor profiles will be summarized.

#### **Analysis of secondary endpoint**

Adverse events will be summarised and listed (SAS).

## **7.2. Sample size**

Due to the conceptual nature of this trial no formal sample size calculation has been performed. It is assumed that 12 healthy volunteers will be adequate for evaluating the data quality of the sensor.

## **7.3. Drop-out**

As this study only consist of one study visit, expected drop-outs are 0. Should there be a drop-out, will these be replaced until 12 patients has finalised visit 1.

## **7.4. Pass/fail criteria**

No formal pass/fail criteria are applied.

## **7.5. Interim analysis**

No interim analysis will be performed.

## **7.6. Statistical reason for termination of investigation**

There is no reason to terminate the investigation based on statistical considerations

## **7.7. Deviation(s) from statistical plan**

Any deviations from the statistical plan will be documented in the clinical report.

# **8. Data management**

## **8.1. Data review, database cleaning, and issuing and resolving data queries**

Data management and statistical analyses is carried out by Medical Affairs, Coloplast A/S.

To ensure correct data entry, data is entered twice (double data entry). Data management is responsible for control of data consistency and for completeness of data from each subject.

Discrepancies are listed in Data Query Forms (DQF), and the Investigator is responsible for solving these promptly. When all DQFs are solved the database is locked and the statistical analyses are performed.

When all DQFs are solved the database is locked and the statistical analyses are performed.

## **8.2. Verification, validation and securing of electronic clinical data systems**

EXPeRT Data Management, version 5.0.05 system delivered by OmniComm Systems Inc. is used for data management. The system is designed to be compliant with the requirements of 21 CFR part 11. It is a validated data management system allowing only qualified and trained personnel to enter the system.

## **8.3. Data retention**

The sponsor file must be archived for a minimum period of 5 years after the final clinical investigation report has been signed.

All investigation site documents must be archived for a minimum period of 5 years after the final clinical investigation report has been signed.

## **9. Amendments to the CIP**

Any significant changes to the CIP are:

- Agreed between sponsor, PI(s) and the coordinating investigator.
- Justified in a statement included in the amended section and the version number and date of amendment must be documented.
- Registered in the Change Log.
- Notified to or approved by the EC before implementation
- Notified to or approved by the regulatory authorities before implementation

Example of significant change: Changes of inclusion criteria, end points or assessment methods.

## **10. Clinical Investigation Plan deviations**

Deviations to Clinical Investigation Plan occurs when the activities during the clinical investigation diverge from the approved investigation plan.

The Investigator is not allowed to deviate from the CIP unless under emergency circumstances and to protect the rights, safety and well-being of the subject(s).

Deviations must be reported to sponsor and deviations affecting the scientific aspect of the investigation or the safety of the subject is reported to the EC and Danish Medicines Agency by sponsor. Deviations not affecting the scientific aspect of the investigation or the safety of the subject will be documented in a "Protocol deviation form" or a "Note To File" and filed in the Investigator Site File and Study Master File.

## **11. Device Accountability**

All access to the investigational devices used in the clinical investigation is controlled by storage procedures and device accountability logs as described below. The investigational devices must only be used in this clinical investigation and only per the CIP.

The investigational site will receive 12 investigational devices – one for each subject and corresponding catheters.

The Investigator or a representative hereof keeps records documenting the receipt, use and return of the investigational devices.

## 12. Statement of compliance

The clinical investigation is conducted in accordance to:

- Ethical principles that have their origin in the Declaration of Helsinki, 1964, Last amended at the 64th WMA General Assembly, Brazil, 2013.
- MDD 93/42/EEC as amended by Directive 2007/47/EC (commonly known as the Medical Device Directive).
- MDR (EU) 2017/745
- ISO 14155:2011 "Clinical Investigation of medical devices for human subjects – Good clinical practices".

Any applicable regional or national regulations will be specified in the country specific CIP

### 12.1. Ethics committee and regulatory authorities

The CIP and/or other relevant documents are submitted to the appropriate EC(s) and regulatory authorities. This clinical investigation will not begin until the required approval from the EC and regulatory authorities have been obtained. Any amendment to the protocol will be submitted to the same EC(s) and regulatory authority.

Sponsor will notify the relevant regulatory authority and EC(s) concerned of the end of the clinical investigation.

### 12.2. Other relevant authorities

### 12.3. Data protection

All information collected during this investigation is owned by Coloplast A/S and is kept strictly confidential. Subjects are identified by an investigation number and the investigation monitor has access to subjects' notes/documentation for source data verification. Monitoring and monitoring findings will be documented in a report to explain and document that the rights and well-being of the subjects are protected, that the reported data are accurate, complete and verifiable from source documents, and that the conduct of the investigation is following the currently approved Clinical Investigation Plan (CIP), including amendments, and with the applicable regulatory requirements. The reports have no subject identification and are kept confidential during the conduct of the investigation and during archiving for 6 years. Subjects remain anonym for data analysis, as the data is blinded correspondingly in the data analysis.

Should the investigation require future review, relevant ethics committees and Coloplast A/S Internal Audit performer will be allowed access to all relevant information for audit purposes.

The allowance of DKK 1200,- is taxable and will be payed to the subject after test visit as cash. The allowance is taxable per local legislations and Coloplast A/S is responsible for reporting the remuneration to the tax authorities. Therefore, it is necessary to collect subject's social security number and hand it over to tax authorities. The number will then be strictly confidentially handled, and only people with relevant interest will have access to the information.

Coloplast A/S complies with applicable data privacy law, including the [EU General Data Protection Regulation \("GDPR"\)](#). Under GDPR the legal basis for Coloplast's collection and use of the personal information is for the purpose of analyzing samples, and all data collected in this clinical investigation.

Coloplast A/S protects all personal information and will only allow it to be used for the mentioned purposes related to only this clinical investigation.

Each subject is entitled to get access to all the data and to have rectified any inaccurate data Coloplast A/S is processing about the subject. All data are collected based on the consent each subject has given when being eligible and enrolled in the investigation. The subject is entitled to withdraw any such consent at any time, and Coloplast A/S will then cease to use such personal information for further innovation and improvement of incontinence products. The already data collected and handled in the investigation will not be retired.

For further information please see Coloplast's Global Privacy Notice ([www.coloplast.com/global/privacy-notice](http://www.coloplast.com/global/privacy-notice))

